9.0 Statistical Considerations

9.1 Aim 1

The primary study outcome is biochemically-verified self-reported 7-day point prevalence abstinence at 6 months as defined by salivary cotinine level < 10 ng/ml or expired CO <10 ppm. A secondary outcome is biochemically-verified self-reported 7-day point prevalence abstinence at 12 months. Brief surveys will be conducted at 6 and 12 months after study enrollment to determine self-reported abstinence. Biochemical validation of smoking status is accomplished via mailed salivary cotinine samples or expired CO.

Analysis:

The effect of MIST vs. UC on biochemically-verified abstinence at 6 months will be estimated via a relative risk of abstinence and tested at a 5% significance level via a chi-squared test with Yates' continuity correction. The same method will be applied

to the secondary outcome at 12 months. Anticipated loss to follow up is accounted for in the expected approximate UC abstinence rates where persons lost to follow up will be treated as non-abstinent. However, sensitivity analyses will consider a range of possible odds ratios (1, 2, and 5) linking loss to follow-up and smoking. [51] Exploratory analyses testing for effect heterogeneity will use multivariate logistic regression models adjusting for the main effect of a potential modifier and testing for an interaction with the effect of MIST. The potential effect modifiers to be explored are age, race, sex, NMR, and pre-intervention plan to quit.

Power:

Conservatively assuming a biochemically validated abstinence rate of 10% under UC, a chi-squared test on 1000 patients (at 6 months) will detect a MIST abstinence rate of 16.2% (Risk Difference=6.2%, Relative Risk=1.62, Odds Ratio=1.74) with 80% power. Assuming a 15% biochemically validated abstinence rate under UC (at 12 months), a 22.2% rate under MIST (RD=7.2%, RR=1.48, OR=1.62) is detectable with 80% power. Power was estimated via simulating 20K datasets under the settings above in the statistical program R and were checked against the simplified estimates of the pwr package.

9.2 Aim 2

A secondary outcome is participant self-reported medication adherence assessed at the 1- and 3-month surveys (Aim 2a). Another secondary outcome is PCP prescriptions for smoking cessation medication after study enrollment for participants who continue to smoke. Pharmacy data from CMS will also be used to supplement participant's self-report of whether they received smoking cessation medication prescriptions from their PCP after study enrollment (Aim 2b) and whether the prescriptions were matched to NMR (Aim 2c).

Analysis:

To account for the longitudinal structure of the data with observations at months 1, 3, 6, and 12, Aim 2 analyses will utilize general estimating equations (GEE) with an autoregressive (AR1) correlation structure adjusting for self-reported smoking status and age, race/ethnicity, education, and dependence (baseline FTND score) in a multivariate logistic GEE model. Each of the following three models will estimate a common odds ratio for MIST vs UC for the outcome of interest. All patients will be included in the analyses and missing covariate data will be multiply imputed via predictive mean matching imputation. Standard errors will be estimated via Rubin's rules and statistical significance tested via Wald tests. Unobserved adherence status or prescriptions will be treated as non-adherent or not received, respectively. H2a: We will estimate the odds ratio for being adherent in the 3 months post-enrollment. H2b: We will estimate the odds ratio for receiving a PCP prescription for a smoking cessation medication in the 12 months post-enrollment. PCP prescriptions occurring between any two time points, e.g. months 3 and 6, will be attributed to the latter time point for analysis. H2c: We will estimate the odds ratio for receiving an NMR-

matching PCP prescription. Exploratory and sensitivity analyses: For each of the three outcomes, exploratory analyses will test for interactions between the MIST effect and month of follow up; and for interactions between the MIST effect and medication type (NRT or varenicline). Sensitivity analyses will vary the correlation structure assumptions to ensure the main conclusions are robust to model specifications.

Power:

For all hypotheses related to clinical implementation, we conservatively estimate power by focusing on the first observation time point. Under a common odds ratio, power will be higher when analyzing all time points together. H2a: Assuming a selfreported adherence rate of 50% under UC, analysis of 1000 patients (at 3 months) will detect a MIST adherence rate of 59.0% (Risk Difference=9.0%, Relative Risk=1.18, Odds Ratio=1.44) with 80% power. H2b: Because self-reported abstinence at a given time point will be a very strong predictor of not receiving a PCP prescription for smoking cessation medication at the following time point, with regard to statistical power the sample sizes will be effectively reduced by the respective quit rates. For this effective sample size reduction, we conservatively assume guit rates of 15% for UC and 25% for MIST. Assuming a PCP prescription rate of 30% under UC, a 39.8% rate under MIST (RD=9.8%, RR=1.33, OR=1.54) is detectable with 80% power. H2c: Similarly, assuming an NMR-matching PCP prescription rate of 15% under UC, a 23.2% rate under MIST (RD=8.2%, RR=1.55, OR=1.71) is detectable with 80% power. Power was estimated via simulating 20K datasets under the settings above in the statistical program R and were checked against the simplified estimates of the pwr package.

9.3 Aim 3

Passive surveillance of 12-month clinical composite outcomes (ER visit, hospitalization, or death) in VUMC and non-VUMC facilities is also conducted by specific members of the research team.

Analysis:

The effect of MIST vs UC on the Aim 3 primary outcome of a healthcare composite outcome consisting of hospitalization, emergency department visit, and/or death within 12 months will be estimated via a relative risk of the composite outcome and tested at a 5% significance level via a Chi-squared test with Yates' continuity correction. The same method will be applied to the secondary outcomes of hospitalization, ED visit, and mortality analyzed separately. Exploratory analyses testing for effect heterogeneity will use multivariate logistic regression models adjusting for the main effect of a potential modifier and testing for an interaction with the effect of MIST. The same modifiers as in Aim 1 will be tested. All analyses will be reported as primary, secondary, or exploratory as specified here.

Power:

The composite health care and mortality outcomes are gathered via VUMC EHR, state vital records, and the existing Tennessee HDDS, thus patients are presumed to not have an event unless one is observed. Conservatively assuming a composite outcome rate of 50% under UC (which is based on EHR estimates from VUMC smokers in care), a Chi-squared test will detect a MIST rate of 41.0% (RD=-9.0%, RR=0.82, OR=0.70) with 80% power. Assuming rates for UC of 10%, 20%, and 30% respectively for mortality, ED visits, and hospitalizations, a Chi-squared test on 1000 patients will detect with 80% power MIST rates of, respectively, 5.1%, 13.2%, and 22.0% (RD=-4.9%, -6.8%, 8.0%; RR=0.51, 0.66, 0.73; OR=0.48, 0.61, 0.66).

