5.3 Inclusion Criteria

Inclusion Criteria

- 18 years old or older
- be enrolled in or pending approval for an insurance plan that supports prescription coverage for smoking cessation medication (including Medicare part D, Medicaid, private insurance, Federal or other governmental, or other insurance) or willing and able to purchase smoking cessation medication and pay for healthcare out of pocket to facilitate delivery of medications
- have a regular provider/PCP or have access to a free or low cost clinic for regular clinical care that can prescribe smoking cessation medication; if patient does not have a PCP, the study team may collaborate with the patient to establish a primary care provider
- agree to quit or try to quit smoking upon study enrollment
- be a daily smoker when smoking normally during the month prior to entering the study
- be medically eligible to use varenicline*
- be medically eligible to use nicotine replacement therapy **
- have received medication recommendations from a tobacco counselor
- agree to take smoking cessation medication (i.e., varenicline OR nicotine replacement therapy) home and consider using it
- have a cell phone or landline that can be reached directly (i.e., without transfer)
- have a permanent address where they live and can receive mail
- estimated life expectancy of at least one year or greater

*Medical eligibility to take varenicline is defined by absence of the following:

- Serious brain condition that impairs cognition (including but not limited to dementia, delirium, brain tumors/metastases, uncontrolled seizures (i.e., seizures within the past 3 mo.))
- pregnancy/planning to become pregnant/breastfeeding in the next year
- history of allergic reaction to varenicline
- unstable/uncontrolled mental health condition:
 - a. altered mental status (e.g., delirium, hallucinations) **OR**
 - b. serious psychiatric symptoms in the past 6 months as defined by suicidal ideation or attempt, hospitalization or ED visit involving a psychiatric condition (e.g., depression, anxiety, bipolar, schizophrenia, schizoaffective disorder, PTSD, substance use (e.g., overdose, other related) **OR**
 - c. changes in psychiatric medication within the past 3 months
- if alcohol use; history of blackouts or seizures with drinking

** Medical eligibility to use nicotine replacement therapy is defined by absence of the following:

- o unstable from cardiovascular perspective

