5.8 Randomization

Patients can be randomized into the study once the NMR test has resulted. Randomization will be stratified on three factors: (1) primary admitting diagnosis (cardiac vs. other); (2) cigarettes/day (≥10, <10); (3) primary insurance (Medicaid, Medicare with Part D, Private Insurance, Federal/Other Governmental/Other Insurance); and (4) NMR status ("normal"/"slow") to ensure that the treatment groups are balanced. After the patient enrolls, the RA will be directed to the electronic randomization screen in REDCap, which, once submitted, automatically assigns the participant to a randomization group.

Blinding: The nature of the study precludes blinding of patients or research staff to the study condition.

Participants will receive a handout describing their assigned treatment. For those randomized to the MIST (precision) arm, the handout will include information on the NMR result and recommended medication. In the event that a participant is enrolled before a valid NMR result is received, study staff may contact the participant via phone/text/email (per participant preference) to notify of randomization status and initiate post-randomization procedures including facilitation of smoking cessation medication. Those randomized to the Usual Care arm will receive their NMR result at study completion, 12 months post-study enrollment; participants in the Usual Care arm who withdraw from the study will not be provided precision care information.

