7.5 Data Safety and Monitoring Board

The Data and Safety Monitoring Board (DSMB) will monitor the MIST trial. The DSMB will act in an advisory capacity to the study PIs to monitor participant safety, data quality and evaluate the progress of the studies being conducted.

The DSMB is responsible for ensuring subject safety (by reviewing blinded and unblinded safety data on a regular basis and assessing the safety of study procedures) and for monitoring the overall conduct of the studies. The DSMB will monitor enrollment, follow up and adverse events.

The DSMB is an independent group advisory to the PI and study team, and is required to provide recommendations about conduct of the trial. In addition, the DSMB is asked to make recommendations, as appropriate, about:

- Benefit/risk ratio of procedures and participant burden
- Selection, recruitment, and retention of participants
- Protocol violations and adherence to protocol requirements
- Completeness, quality, and analysis of measurements
- Amendments to the study protocol and consent forms
- Participant safety
- Notification of and referral for abnormal findings

The DSMB will consist of 3 members and strong consideration will be given to include at least one investigator with expertise in smoking cessation, 1 statistician, and 1 investigator with expertise in clinical trials. The DSMB will meet twice during the course of the study, which will be scheduled after approximately one third and approximately two thirds of the target number of participants have reached the final outcome. The DSMB has the authority to assess the option of stopping early for overwhelming benefit demonstrated in the primary study endpoint, or for safety concerns. The panel will make recommendations about the continuation, modification, or termination of the study to the study steering committee. Unscheduled meetings can be requested by any party with the responsibility of overseeing the study.

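### Free improvement: the Yates correction runs the primary test at about 3.8% rather than 5%, and the analysis ignores the factors used to stratify randomisation

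*Combined protocol and SAP*

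**What the plan says.** Section 9.1 estimates the MIST effect on verified abstinence at 6 months as a relative risk, "tested at a 5% significance level via a chi-squared test with Yates' continuity correction", and applies the same method at 12 months. Section 9.3 repeats it for the healthcare composite and its components: "tested at a 5% significance level via a Chi-squared test with Yates' continuity correction". Neither section says how the interval for the relative risk is formed.

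Section 5.8 states that "Randomization will be stratified on three factors" and then lists four: admitting diagnosis (2 levels), cigarettes per day (2), primary insurance (4) and NMR status (2). The stated purpose is "to ensure that the treatment groups are balanced". None of the four enters the primary or secondary analysis in Aim 1 or Aim 3. NMR appears only as one of several exploratory effect modifiers.

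The Aim 2 model in section 9.2 adjusts for smoking status, age, race/ethnicity, education and "dependence (baseline FTND score) in a multivariate logistic GEE model". FTND covers cigarettes per day in part; diagnosis, insurance and NMR status are absent.

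The power figures in section 9.1 come from simulation and "were checked against the simplified estimates of the pwr package".

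**The concern.** There are two separate points.

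**The correction.** Yates' adjustment makes the chi-squared test mimic Fisher's exact test. With about 500 per arm and a 10% event rate the uncorrected test already holds its level, so the correction only spends power. It can also set the test against the estimate: an ordinary 95% interval for the relative risk can exclude 1 while the Yates p-value exceeds 0.05.

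**The strata.** Stratified randomisation removes chance imbalance on the chosen factors, but an unadjusted test still counts that imbalance in its variance. The test is then conservative to the extent that the factors predict abstinence. In Aim 2 the omission of NMR status matters most for H2c, because NMR status defines what counts as a matched prescription and so may change the chance of a match.

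At stake is efficiency and a clean match between design, test and interval, not validity.

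**Working it through.** **Inputs.** From section 9.1: 1,000 patients, 5% level, 10% against 16.2% at 6 months, 15% against 22.2% at 12 months, 80% power for each. From section 9.3: the Aim 3 rates. Assumed, because not stated: 1:1 allocation, so 500 per arm, and one final look.

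**Formula.** With a and b events in arms of n₁ and n₂, N = n₁ + n₂ and m = a + b,

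X² = N·(|a(n₂ − b) − b(n₁ − a)| − c)² / [n₁·n₂·m·(N − m)],

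with c = N/2 for Yates (the bracket set to zero if negative) and c = 0 without. Reject if X² > 3.84. Size and power are the summed binomial probabilities of rejection over all 501 × 501 tables.

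**The plan's own figure.** The Yates test gives exact power of 80.8% at 6 months and 81.5% at 12 months, which fits the stated 80%. The uncorrected test gives 83.2% and 83.5%, and the uncorrected arcsine approximation gives 83.3% at 6 months. The stated 80% therefore belongs to the Yates test.

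**Size**

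| Common rate | Yates | Uncorrected |
|---|---|---|
| 10% | 3.84% | 4.96% |
| 15% | 4.06% | 4.96% |
| 50% | 4.63% | 5.37% |

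**Power**

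| UC vs MIST | Yates | Uncorrected |
|---|---|---|
| 6 months, 10% vs 16.2% | 80.8% | 83.2% |
| 12 months, 15% vs 22.2% | 81.5% | 83.5% |
| Composite, 50% vs 41.0% | 80.5% | 82.2% |
| Mortality, 10% vs 5.1% | 81.1% | 84.2% |
| ED visits, 20% vs 13.2% | 80.5% | 82.6% |
| Hospitalisation, 30% vs 22.0% | 80.5% | 82.4% |

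The Yates test reaches 83.2% at 6 months only with 532 per arm: 2 × (532 − 500) = 64 more patients. The MIST rate detectable from 10% with 80% power is 16.1% with Yates and 15.9% without.

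**Test against interval.** Take 71/500 against 50/500. RR = 1.42 and SE(log RR) = √(1/71 − 1/500 + 1/50 − 1/500) = 0.173, so the ordinary 95% interval is 1.01 to 1.99. Here |a(n₂ − b) − b(n₁ − a)| = 71·450 − 50·429 = 10,500, and the denominator is 500·500·121·879 = 2.659 × 10¹⁰.

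- Uncorrected: 1000·10,500²/2.659 × 10¹⁰ = 4.15, p = 0.042.
- Yates: 1000·10,000²/2.659 × 10¹⁰ = 3.76, p = 0.052.

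At 10% against 16.2% this conflict arises in 2.1% of trials. The same interval disagrees with the uncorrected test in 0.3%. The log-RR interval is an assumption.

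**Strata.** The documents do not say how prognostic the factors are, so a range was simulated: 20,000 trials per setting, 2 × 2 × 4 × 2 = 32 cells, permuted blocks of 4, overall rates held at 10% and 16.2%. Assumed shares: normal NMR 62%, 10 or more cigarettes per day 65%, cardiac 25%, insurance 30/35/25/10%. The adjusted test uses the standardised risk difference from a logistic model with main effects.

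| Assumed SD of log-odds between strata | Power: Yates / uncorrected / adjusted | Size: Yates / uncorrected / adjusted |
|---|---|---|
| 0 | 80.4 / 83.0 / 83.1% | 3.9 / 5.1 / 5.1% |
| 0.3 | 80.5 / 83.1 / 83.4% | 3.9 / 5.1 / 5.2% |
| 0.5 | 80.9 / 83.3 / 84.2% | 3.6 / 4.7 / 4.9% |
| 0.8 | 81.6 / 84.1 / 86.0% | 3.2 / 4.3 / 5.0% |

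Monte Carlo SE is at most 0.3 points for power and 0.2 for size. Adjustment thus adds 0.1, 0.3, 0.9 and 1.9 points over the uncorrected test. A separate simulation with a Cochran-Mantel-Haenszel test (10,000 trials per setting, slightly different assumed shares) gave gains of about 0, 0.6 and 2.8 points when the strata explained 0%, 2.5% and 10% of outcome variance, with size between 4.9% and 5.4%.

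**The case against.** The strongest reply is that nothing is broken. A 5% test must not exceed 5%, and Yates does not. The power claim is honest, and the detectable rate moves by only 0.2 points. All of that stands, and it is why this is an improvement and not an error.

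A second objection is that the slack gives some protection while section 7.5 lets the DSMB consider "stopping early for overwhelming benefit demonstrated in the primary study endpoint" with no boundary. In an illustrative worst case, testing at 5% at each of three looks with a 10% rate, overall error is about 7.8% with Yates and 10.7% without; with a strict interim limit of p < 0.001 it is about 3.9% and 5.0%. This stands as a reason to fix a boundary. It is no reason to keep the correction, since Yates does not hold 5% in that worst case either.

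Third, the gain from the strata rests on assumed prognostic strength and could be nil. True, which is why it is given as a range; size stayed close to 5% throughout.

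Fourth, near a 50% rate the uncorrected test runs at 5.4% and Yates at 4.6%, so the case is weaker for the Aim 3 composite. That stands; Aim 3 is exploratory, and the size of the adjusted test was not computed there.

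Fifth, adding covariates to the logistic GEE changes the conditional odds ratio being estimated, and no computation supports the Aim 2 request. Both are right. That request rests on matching the analysis to the design.

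Last, the trial is open-label, so a late change of primary test could look opportunistic. This bears on timing: the change has to precede any comparison of outcomes by arm.

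**Conclusion.** The concern holds as an improvement that needs no extra patients. At the planned 10% rate the primary test has a true size of 3.8%. Dropping the correction restores 5.0% and raises power by 83.2 − 80.8 = 2.4 points at 6 months and 83.5 − 81.5 = 2.0 points at 12 months. These figures are exact, given 500 per arm and a single look. Using the stratification factors adds between nothing and about 2 to 3 points more; that range rests on assumed prognostic strength and factor shares. The plan as written remains valid and adequately powered. The change should be made, with medium confidence overall because the second gain cannot be sized from the documents.

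**What to change.** 1. In section 9.1, drop the Yates correction. Make the primary analysis a logistic model with arm and main effects of the four stratification factors. Report the standardised relative risk and risk difference with robust 95% confidence intervals, and take the p-value from that same analysis.
2. Use main effects, since 32 cells would be sparse, and fix a rule in advance for pooling small insurance levels.
3. Do the same at 12 months and in Aim 3. Keep the Yates test as a sensitivity analysis; the unadjusted table can still be shown.
4. Add the stratification factors to the Aim 2 GEE, NMR status above all for H2c.
5. In section 5.8, reconcile the stated count of factors with the four listed. Analyse insurance as recorded at randomisation. Section 5.3 admits patients who "be enrolled in or pending approval for an insurance plan" and patients who pay out of pocket, so state which level holds patients whose coverage is pending and which holds self-payers.
6. If the DSMB looks for benefit are given a boundary, use the same statistic at every look.

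The cost is SAP wording and a few lines of code, with no new data. The insurance coding has to be settled first, and the whole change fixed before outcomes are compared by arm.

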To demonstrate feasibility of this proposal, we conducted and published a pilot RCT of 81 adult daily smokers with medical comorbidity to a metabolism-informed intervention vs. a robust control, established infrastructure to track participants, and collected outcome data. [36] Participants reported perceptions of the metabolism-informed intervention, underwent blood draw for NMR, and received expert cessation counseling. For intervention participants, medication selection was informed by NMR result (normal (≥ 0.31) vs. slow (< 0.31)) using the threshold by Tyndale and colleagues. [5] The primary outcome was feasibility of offering NMR in a clinical population, reflected by attitudes toward the precision intervention and by match rates between NMR and medication. Secondary endpoints (cessation, confidence, medication use, smoking status) were assessed over 6 months for feasibility. The median NMR for slow metabolizers was 0.22 [0.18–0.27] and for normal metabolizers was 0.54 [0.38– 0.82], similar to the distribution observed in the literature.[5] Over 90% of participants endorsed the idea of metabolism informed care and all but two were prescribed medication. Despite very high varenicline prescription rates of \sim 60% in both treatment arms, NMR-medication matching was markedly higher among intervention (36/43; 84%) versus control (21/36; 58%) participants. Put another way, 42% of control participants were "mismatched," as compared to only 16% in intervention (p = 0.02). At the 6 month follow up time point, 80% of participants were reached. While this pilot RCT was not powered for abstinence, medication adherence, or other cessation-related outcomes, these were assessed as part of the feasibility of outcome data collection. Self-reported rates of medication use and side effects at 3 months, and 7-day point prevalence abstinence at 6 months, did not differ statistically between treatment arms. From this pilot study we concluded that: (1) Smokers viewed the metabolism informed treatment favorably and were willing to use medication based on NMR test results, with 3-fold increased concordance (matching) between nicotine metabolism status and medication in the intervention arm; at the same time, (2)Nearly 1/2 of patients in UC received medications that were not matched with their NMR, underscoring the generic nature of UC despite high prescription rates of varenicline in both treatment arms of the study.

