Aim 1: Biochemical Verification of Self-Reported Abstinence (Table 2, Row 1) For participants who self-report abstinence at the 6 month and/or 12 month follow up surveys, study staff will attempt to biochemically-verify the self-report. Based on prior experience with challenges in obtaining biochemical verification, there will be several options including: (1) saliva cotinine (in- person or mailed); (2) end-expired carbon monoxide (in-person or remote) if participants are unwilling or unable to verify with cotinine (e.g., actively using NRT). Standard saliva cotinine kits will be analyzed by Salimetrics Laboratory or other comparable lab. Smoking abstinence can also be confirmed through in-person or remote carbon monoxide (CO) testing (if a participant is on NRT). If a participant is unable to complete an in-person CO, then a personal CO device (such as a CoVita iCO Smokerlyzer) may be mailed to the participant to complete the CO reading remotely. We have successfully used this protocol for mailed cotinine samples and CO testing in the past. Smoking abstinence will be defined conservatively according to recommended standards. The following cessation milestones will be assessed in addition to point prevalence abstinence (PPA):

- i. *Initial abstinence* is defined as the first instance in which the participant refrains from smoking for at least 24 hours; duration of initial abstinence will also be assessed.
- ii. *Initial lapse,* defined as the first episode of ANY smoking, even a puff, after achieving initial abstinence, will also be assessed.
- iii. Continuous abstinence is defined as no smoking, even a puff, since study enrollment (i.e., achieved PPA at 1, 3, 6, and 12 mo +no smoking in between surveys + biochemical validation of selfreported (SR) PPA at 6, 12 mo). Participants who are unable to biochemically verify abstinence will be assumed to be smoking, by convention, but sensitivity analyses will consider a range of possible odds ratios (1, 2, and 5) linking loss to follow-up and smoking. [51]

| Table 2: Main Ou | itcome Measures by Study | y Aim | | | | |
|-----------------------------------|--|--------------|---|--|--|--|
| Outcome | Measure | Data sources | | | | |
| | | Survey | Other source | | | |
| AIM 1: | SR at 1, 3, 6, 12 m | | | | | |
| Abstinence | Biochem. validation at 6 m (primary study | Х | 12 m* via saliva cotinine <10 ng/ml or expired CO <10ppm | | | |
| AIM 2. | SR at 1 3 6 12 m | | | | | |

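### The missing-outcome check gives both arms one list of odds ratios; used within arm with similar follow-up, it cannot challenge a positive result, and a UC by MIST grid would

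*Combined protocol and SAP*

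**What the plan says.** Section 9.1 defines the endpoint: "The primary study outcome is biochemically-verified self-reported 7-day point prevalence abstinence at 6 months". The effect is to be "estimated via a relative risk of abstinence and tested at a 5% significance level", using a chi-squared test with Yates' correction. For missing outcomes, "persons lost to follow up will be treated as non-abstinent". The planned check is that "sensitivity analyses will consider a range of possible odds ratios (1, 2, and 5) linking loss to follow-up and smoking", with one methods paper cited.

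Section 5.9 repeats the list. There, participants "unable to biochemically verify abstinence will be assumed to be smoking, by convention, but sensitivity analyses will consider a range of possible odds ratios", with the same three values and the same citation. That sentence sits under the continuous-abstinence item.

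Neither section assigns odds ratios to arms, names the rate to which an odds ratio is applied, or gives a variance method. Section 9.2 does name a method, but for Aim 2: "missing covariate data will be multiply imputed via predictive mean matching imputation", with Rubin's rules for the standard errors. On blinding, section 5.8 says: "The nature of the study precludes blinding of patients or research staff to the study condition".

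**The concern.** A sensitivity analysis for missing outcomes should vary the assumption that could undo the result. Here the effect measure is a ratio between arms. Raising or lowering the quit rate among the missing by the same rule in both arms shifts numerator and denominator together, so the ratio can stay almost still while the absolute rates move. What could change the ratio is missingness that means something different in MIST and in UC. Participants and staff know the allocation, so that is possible. The listed values, used one at a time in both arms, do not examine it.

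The result also depends on a step that the text leaves open. Applying an odds ratio to each arm's own rate and applying it to a pooled rate give different answers. If the choice is made once results by arm are known, the more reassuring version could be picked.

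**Working it through.** **Inputs.** From section 9.1: 1000 patients, 10% abstinent under UC and 16.2% under MIST at 6 months (losses already counted as smoking), 5% level, Yates' correction. Assumed: 1:1 allocation, so 500 per arm (50 and 81 quitters at the design effect), and 80% followed in each arm. The plan gives no loss rate for this trial; section 3.0 says of the pilot: "At the 6 month follow up time point, 80% of participants were reached".

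**Plan's own figure.** Enumerating all results at 10% and 16.2% with 500 per arm gives 80.8% power, against the stated 80%. It reproduces.

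**Method.** In an arm with q quitters, n=500 and followed fraction f:
- observed rate r = q/(n·f);
- quit odds among the missing = [r/(1−r)]/OR, converted to a rate m;
- arm total = q + n(1−f)·m.

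The relative risk (RR) and Yates p are then recomputed on these expected counts. In the pooled version, r is the rate over both arms' followed participants.

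**Example, OR 2 within arm, 50 vs 81.** UC: r = 50/400 = 0.125, odds 0.1429, halved 0.0714, m = 0.0667, total 50 + 6.67 = 56.67 (11.33%). MIST: r = 81/400 = 0.2025, m = 0.1127, total 81 + 11.27 = 92.27 (18.45%). RR = 18.45/11.33 = 1.63. With OR 1 and equal f, each arm's total is q/f, so RR is exactly the primary one.

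**Results, 80% followed in each arm.**

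| Odds ratios | 50 vs 81 (primary RR 1.62, p=0.005) | 50 vs 73 (primary RR 1.46, p=0.034) |
|---|---|---|
| Common, within arm: 1 / 2 / 5 | RR 1.62 / 1.63 / 1.63; p 0.001 / 0.002 / 0.003 | RR 1.46 / 1.47 / 1.46; p 0.015 / 0.021 / 0.027 |
| Common, pooled rate: 1 / 2 / 5 | RR 1.47 / 1.53 / 1.58; p 0.010 / 0.008 / 0.006 | RR 1.35 / 1.39 / 1.43; p 0.054 / 0.045 / 0.039 |
| UC 1, MIST 2 | RR 1.48; p 0.012 | RR 1.33; p 0.080 |
| UC 1, MIST 5 | RR 1.37; p 0.047 | RR 1.24; p 0.21 |
| Other direction | UC 5, MIST 1: RR 1.92; p<0.001 | UC 2, MIST 1: RR 1.61; p 0.003 |

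**Imputation variance.** Expected counts treat imputed outcomes as observed. With multiple imputation, Rubin's rules and a Wald test on log RR, 50 vs 81 gives p=0.019 for UC 1 / MIST 2 and about 0.056 to 0.058 for UC 1 / MIST 5. For 50 vs 73, a common odds ratio gives p=0.025 to 0.027, against a plain Wald p of 0.028 on the primary counts. The fall from 0.034 in the table is therefore mostly a matter of test and variance.

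**Tipping point with UC at 1 (expected counts).** Significance is lost at a MIST odds ratio of about 5.4 for 50 vs 81, and 1.56 for 50 vs 73. With 50 UC quitters, UC 1 / MIST 2 removes significance only at 72 to 75 MIST quitters (RR 1.44 to 1.50).

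**Share of significant primary results that lose significance** (all results at 10% and 16.2%, no imputation variance; common lists count a loss at any of 1, 2, 5):

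| Followed, UC / MIST | Common, within arm | Common, pooled | UC 1, MIST 2 |
|---|---|---|---|
| 90% / 90% | 0% | 3% | 7% |
| 80% / 80% | 0% | 7% | 14% |
| 60% / 60% | 0% | 18% | 28% |
| 75% / 85% | 20% | 43% | not used |

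At 80% in each arm, UC 1 / MIST 5 gives 37%.

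**Unequal follow-up, common value within arm, 50 vs 81.** With 75% of UC and 85% of MIST followed, OR 1 gives (81/0.85)/(50/0.75) = 95.29/66.67 = 1.43; OR 2 gives 1.51 and OR 5 gives 1.57.

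**The case against.** The strongest reply is that a nearly unchanged ratio is the right answer when follow-up is equal and missingness means the same in both arms, because counting the missing as smoking then hardly biases the relative risk. The list does test unequal loss, which is a real threat. All of that stands. A reader might infer that the check is empty, or that the open choice alone decides whether it can ever alter the conclusion. The figures do not support this. Within arm, the common list moves the ratio when follow-up differs, and it can carry a near-miss across 0.05: 50 vs 71 quitters goes from p=0.052 to 0.026, 0.034 and 0.043 on expected counts. Such shifts shrink once imputation variance is included (50 vs 70 gives about 0.049 to 0.051).

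Second, the cited paper may settle how the odds ratios are applied. Its title mentions multiple imputation, and nothing more of it is in the documents. So the point is that the plan's text is silent, not that no method exists. The ancillary study in section 5.9 also contemplates extending imputation with health-record smoking status, but only as a possibility.

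Third, both arms share the consult, automated calls, survey schedule and payments, so differential missingness is a conjecture. That also stands: the documents do not show it.

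Fourth, section 5.9 already links the odds ratios to participants who cannot verify abstinence. That partly answers whether unverified self-reported quitters are covered; section 9.1 speaks only of loss to follow-up.

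**Conclusion.** The concern holds in a limited form. The plan gives one list for both arms, and its own text states neither the reference rate nor the variance. If a common value is applied within arm and follow-up is similar, the check cannot challenge a positive result: the relative risk stays at 1.62 to 1.63 at the design effect, and 0% of significant results are overturned at 60%, 80% or 90% followed. It is not inert in other settings.

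An arm difference in missingness would matter mainly near the threshold. At the design effect, a twofold odds ratio in MIST alone leaves p=0.012, and it takes about a fivefold one to reach 0.05. A reader might go further and infer that the primary analysis is biased or that a positive finding would be fragile; nothing in the documents establishes either.

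The sizes rest on assumed 1:1 allocation and 80% follow-up. The latter is the pilot's contact rate among 81 people, not completeness of verified outcomes. The overturning shares ignore imputation variance.

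**What to change.** In section 9.1, pre-specify a UC by MIST grid of odds ratios (1, 2, 5 and all missing counted as smoking in each arm), applied within arm by multiple imputation with Rubin's rules. Show both directions, and report the combination at which significance is lost. The common-value list remains as the grid's diagonal.

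State that the grid also covers participants who report abstinence but give no sample, as the section 5.9 sentence suggests; show them as a separate category, and align the wording of the two sections.

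The primary analysis does not change and no new data are needed. The cost is a short text amendment, some analysis time, and a longer sensitivity table that may show the result to be less robust than the common list would.
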